3 LIST OF ABBREVIATIONS

AE	Adverse Event
BID	Twice Daily
CBC	Complete Blood Count
CMP	Comprehensive Metabolic Panel
CRF	Case Report Form
CTCAE	Common Terminology Criteria for Adverse Events
ET	Early Termination
FDA	Food and Drug Administration
HCG	Human Chorionic Gonadotropin
ICH	International Conference on Harmonization
IGA	Investigator's Global Assessment Scale
IL	Interleukin
IND	Investigational New Drug
IRB	Institutional Review Board
ITT	Intent-to-Treat
IV	Intravenous
Mn	Manganese
NOAEL	No Adverse Effect Level
PK	Pharmacokinetic
PRN	Pro re nata, When Necessary
PRO	Patient Recorded Outcome
QD	Once Daily
SAE	Serious Adverse Event
SAP	Statistical Analysis Plan
SOC	System Organ Class
UV	Ultraviolet
WIRB	Western Institutional Review Board

4 SYNOPSIS

Protocol Title:

An Exploratory Trial to Evaluate the Clinical Effectiveness of a Topical Application of BMX-010 in Subjects with Acne Vulgaris

Protocol Number: BMX-DERM-203	Phase: 2
Protocol Version: 1.0	
Test Drug: BMX-010	Indication: Acne Vulgaris

Number and Country of Study Sites: Up to 20 study centers in the United States.

Objectives:**Part A****Primary Objectives**

1. Determine whether the optimum frequency of topical application of BMX-010 0.03% is once per day or twice per day for a treatment interval of 7 to 28 days.
2. Determine whether the optimum frequency of topical application of BMX-010 0.1% is once per day or twice per day for a treatment interval of 7 to 28 days.
3. Determine if BMX-010 cream or gel provides better efficacy.
4. Evaluate the efficacy of BMX-010 0.03% in treatment of Acne Vulgaris.
5. Evaluate the efficacy of BMX-010 0.1% in treatment of Acne Vulgaris.

Secondary Objectives

1. Document, as possible, the clinical effects of BMX-010 in subjects with Acne Vulgaris through clinical photography.
2. Assess the mean percent reduction change in inflammatory and noninflammatory lesion counts from baseline to end of study.

Part B**Primary Objectives**

1. Evaluate the efficacy of BMX-010 compared to placebo in a randomized, double-blind trial.
2. Determine the percent of subjects showing a 2 grade improvement in IGA score after treatment with BMX-010 compared to Placebo.
3. Determine the percent of subjects showing a 2 grade improvement in IGA score with full or partial clearing (final IGA score of 1 or 0) after treatment with BMX-010 compared to Placebo.
4. Determine the time to full clearing of Acne Vulgaris after initiation of treatment with BMX-010.

Secondary Objectives:

1. Determine the percent of subjects showing a 1 grade improvement in the IGA score.
2. Document, as possible, the clinical effects of BMX-010 in subjects with Acne Vulgaris through clinical photography.
3. Assess the mean percent reduction change in inflammatory and noninflammatory lesion counts from baseline to end of study.

Study Design:

This is a Phase 2 clinical trial of BMX-010 in adult men and women with Acne Vulgaris which will be studied in two parts (Part A and Part B). Part A will involve up to 60 subjects treated with either BMX-

010 0.03% or 0.1% given QD or BID for a minimum of 7 days and a maximum of 28 days. Information learned from Part A will be used to design Part B.

Part B is a randomized, double-blind, multi-center, placebo-controlled study of adult men and women with Acne Vulgaris. Subjects will be randomized and dosed with BMX-010 0.03% or 0.1% with the frequency of dosing (either QD or BID) for each dose of the study drug as determined optimal in Part A of this trial. Dosing will occur for a minimum of 7 days and a maximum of 28 days. An overview of the study design is presented in the schematics below, and details of study activities are provided in **Table 4a**.

In the Part A study, up to a total of up to 60 evaluable subjects with Acne Vulgaris will be dosed with BMX-010 (0.03% or 0.1%) topically applied either QD or BID. All subjects will dose for a minimum of 7 days and a maximum of 28 days. The dosing strength, formulation, frequency, and time frame will be at the discretion of the local clinician.

The sponsor may close enrollment once enough data has been obtained to determine the optimal dosing frequency and duration of dosing for each concentration (0.03% or 0.1%) of BMX-010 cream or gel to be studied in Part B.

In the Part B study, up to 150 evaluable subjects with Acne Vulgaris will be dosed with the concentration and formulation of BMX-010 determined optimal in Part A or Placebo given at the frequency determined optimal in Part A. The randomization scheme is 2:1, study drug : Placebo. All subjects will dose for a minimum of 7 days and a maximum of 28 days.

The sponsor may close enrollment once enough data has been obtained to assess the expected efficacy of 0.03% BMX-010 and 0.1% BMX-010. This data will be used to plan future studies.

The Investigator Global Assessment (IGA) is a five scale (0 to 4) static evaluation of overall Acne Vulgaris severity (as described below).

Investigator Global Assessment (IGA) Scale

Grade	Description
0 = Clear	Clear skin with no inflammatory or noninflammatory lesion
1 = Minimal	Almost clear, rare noninflammatory lesions with no more than one small inflammatory lesion
2 = Mild	Mild, some noninflammatory lesions, no more than a few inflammatory lesions
3 = Moderate	Moderate, up to many noninflammatory lesions and may have some inflammatory lesions, but no more than one small nodular lesion
4 = Severe	Severe, up to many noninflammatory and inflammatory lesions, but no more than a few nodular lesions

Although acne occurs on the face *and* trunk, efficacy assessment by IGA will be limited to the face as that is the most frequent site of involvement. However, the study product may be applied to all affected areas during this clinical trial.

Inflammatory and noninflammatory lesions on the face will be counted and reported separately. All lesions on the face, including the nose should be counted.

Subjects will also be asked a series of patient-reported outcome questions and will be asked to consent to optional photographs of the treated lesions.

Throughout both phases, subjects will be queried regarding adverse events (AEs), concurrent medical history and concomitant medication usage.

Subject Population:

Male or female at least 18 years of age with a clinical diagnosis of mild to severe facial Acne Vulgaris.

Inclusion Criteria:

1. Male or female, at least 18 years of age;
2. A clinical diagnosis of mild to severe facial Acne Vulgaris; Subjects may also have acne at other body sites;
3. Screening and Baseline IGA score ≥ 2 (greater than or equal to 2);
4. Willing to refrain from using any topical or systemic treatments for inflammatory skin disease, other than the investigational product;
5. Candidate for topical treatment of Acne;
6. If a cleanser, moisturizer or sunscreen is needed during the study, Subjects must be willing to use only allowed cleansers, moisturizers, sunscreens, or moisturizer/sunscreen combination products. If the subject wears makeup they must agree to use non-comedogenic makeup.
7. Females of child-bearing potential must have a negative urine pregnancy test within 48 hours prior to the first drug administration;
8. Females of child-bearing potential must be willing to use 2 methods of contraception deemed adequate by the investigator (for example, oral contraceptive pills plus a barrier method) through the trial and for 1 month thereafter to be eligible for, and continue participation in, the study;
9. Ability to complete the study in compliance with the protocol, including agreement in writing to apply study product only to the assigned areas; and
10. Ability to understand and provide written informed consent.

Exclusion Criteria:

1. Any underlying disease(s) or some other dermatological condition of the face that requires the use of interfering topical or systemic therapy or makes evaluations and lesion count inconclusive;
2. Use of androgen receptor blockers (such as spironolactone or flutamide);
3. Severe cystic acne, acne conglobata, acne fulminans, or secondary acne;
4. Use of phototherapy devices, energy-based devices, adhesive cleansing strips, or cosmetic procedures (e.g., facials, peeling, comedo extraction) in the past week;
5. Presence of beard or excessive facial hair at Screening which would interfere with the study treatments or study assessments and refusal to remove for duration of study;
6. Prior or current concomitant therapies that would interfere with assessments in the study;
7. Subjects with any underlying disease that the Investigator deems uncontrolled, and poses a concern for the subject's safety while participating in the study;
8. Use of anti-inflammatory medications, salicylic acid; corticosteroids, antibiotics, antibacterials (including benzoyl peroxide-containing products [e.g., benzamycin]), retinoids; other topical acne treatments (e.g., photodynamic therapy, medicated soaps such as those containing benzoyl peroxide, salicylic acid, sulfur, or sodium sulfacetamide) in the past 2 weeks;

9. Oral retinoid use (e.g., isotretinoin) within 6 months prior to baseline or vitamin A supplements greater than 10,000 units/day within 6 months of baseline;
10. Concomitant skin disease that could confound clinical evaluations or increase risk to the subject;
11. Use of medicated make-up (including anti-aging make-up) throughout the study;
12. Use during the study of 1) systemic steroids, 2) topical retinoids to the face, 3) antibiotics known to impact acne, 4) immunosuppressive agents, or immunomodulators;
13. Facial use of 1) topical steroids, 2) topical anti-inflammatory agents, 3) topical antimycotics, 4) any topical acne treatments or 4) topical antibiotics;
14. Use of medicated cleansers on the face (throughout the study);
15. Use of topical astringents or abrasives, medical topical preparations (prescription and OTC products) within 2 days prior to Baseline and throughout the study;
16. Systemic or skin infection requiring antimicrobial therapy;
17. Systemic chemotherapy or radiotherapy within 4 weeks of the Baseline Visit;
18. Immunocompromise of any cause, known human immunodeficiency virus infection, or acquired immunodeficiency syndrome;
19. Pregnancy, planned pregnancy, lactation, or inadequate contraception as judged by the investigator;
20. Active drug or alcohol dependence;
21. Significant acute or chronic medical, neurological, or psychiatric illness that, in the judgment of the investigator, could compromise subject safety, limit the subject's ability to complete the study, and/or compromise the objectives of the study;
22. Previous clinical trial participation for the indication being treated in this protocol.

Dose Regimen/Route- Duration of Treatment and Follow up:

Part A

Subjects will be assigned by the local clinician to receive topical administration of either 0.03% BMX-010 or 0.1% BMX-010, to apply to Acne Vulgaris on the face. Topical therapy with BMX-010 will be either QD or BID as assigned by the local clinician. The planned treatment duration is a minimum of 7 days and a maximum of 28 days. Completion of 28 days of treatment will be recommended to all subjects; however, subjects who have full clearing of the Acne Vulgaris, as determined by the clinical center investigator, may stop study drug therapy and remain in the study with a final evaluation at Day 29 or Day 43 (at the discretion of the investigator).

Part B

Subjects will be randomized 2:1 to receive topical administration of BMX-010 or Placebo which will be dosed at the concentration, formulation, and frequency as defined by Part A. Study product will be applied liberally to Acne Vulgaris on the face. The planned treatment duration is a minimum of 7 days and a maximum of 28 days. Completion of 28 days of treatment will be recommended to all subjects; however, subjects who have full clearing of the Acne Vulgaris, as determined by the clinical center investigator, may stop therapy and remain in the study with a final evaluation at Day 29 or Day 43 at the discretion of the investigator. There will be weekly visits with follow-up done at approximately Days 8, 15, 22, 29 and 43.

Dosage Form and Strength Formulation:

BMX-010

BMX-010 will be supplied at concentrations of 0.03% and 0.1%. BMX-010 will be manufactured by Albany Molecular Research, Inc. (AMRI), and formulation and packaging is done by Velesco Pharmaceutical Services, LLC. BMX-010 is yellow/brown in color and transient (up to 7 days) of yellow discoloration of skin can occur. BMX-010 is dispensed in approximately 10 mL tubes.

Placebo

The Placebo will consist of a formulation containing the same excipients as the active drug product. The Placebo will be color-matched to the active study drug. Placebo will be supplied in 10 mL tubes. Formulation and packaging of the Placebo is done by Velesco Pharmaceutical Services, LLC.

Criteria for Evaluation:

Clinical Efficacy

Clinical effectiveness will be evaluated using the Five-scale IGA for Acne Vulgaris at baseline and end of study, Patient-reported outcomes, and counts of inflammatory and noninflammatory lesions.

Safety Assessments

Safety will be assessed via AE monitoring, concomitant medication monitoring, physical examinations, vital signs, clinical safety laboratory evaluations (complete blood count and chemistry), and pregnancy testing (if applicable).

Table 4.a Schedule of Observations and Procedures

Assessment	Screening ⁷	Treatment Period						Follow-up	
	Day -14 to Day -1	Baseline Day 1	Day 8 (+/- 2 days)	Day 15 (+/- 2 days)	Day 22 (+/- 2 days)	Day 28 ⁸	Day 29 (+/- 2 days)	Day 43 (+/- 2 days)	Follow-up ⁹
Informed consent	X								
Inclusion/exclusion criteria	X	X							
Medical history/demographics	X								
Concurrent medical conditions	X	X	X	X	X		X	X	
Medication history	X								
Concomitant medications	X	X	X	X	X		X	X	
Physical examination, including vital signs and weight ¹	X	X	X	X	X		X	X	
Height	X								
IGA ²	X	X	X	X	X		X	X	
Lesion Counts (Face)		X	X	X	X		X	X	
PRO questions ³			X	X	X		X	X	
Clinical safety laboratory assessments ⁴		X						X	
Urine pregnancy test ⁵	X							X	
Randomization *Part B only		X							
Dosing ⁶		X	X	X	X	X			
Discoloration Review			X	X	X		X	X	
Photographs (optional)		X	X	X	X		X	X	
Pre- and post-treatment AE monitoring	X	X	X	X	X		X	X	

¹ Includes sitting blood pressure, pulse rate and temperature.

² IGA is the 5-point scale as defined in this protocol.

³ All subjects will be asked questions regarding the study drug, clearing and color, these are the Patient Reported Outcome (PRO) questions (see Appendix A).

⁴ Clinical safety laboratory assessments will include CBC with differential and CMP.

⁵ Females of child-bearing potential must have negative results within 48 hours prior to start of drug treatment for inclusion. The Day 43 test is performed for females of child-bearing potential who receive at least one application of study drug.

⁶ In Part A, subjects who meet the inclusion/exclusion criteria will be dispensed BMX-010 gel or cream (concentration and formulation provided to be at the discretion of the local clinical investigator). In Part B, subjects will be randomized to BMX-010 (0.03% or 0.1%) or Placebo (2:1 active:placebo); In Part A, study drug will be applied topically QD or BID at the discretion of the local clinical investigator. In Part B, the dosing frequency will be set as defined from Part A. Dosing will be applied to all active lesions for a minimum of 7 days and up to Day 28.

⁷ The screening and baseline visits may be combined.

⁸ Day 28 is not a clinic day. The subject should stop dosing on Actual Day 28 of the study.

⁹ After the Day 43 final clinic visit, the clinical center may call or mail the subject at approximately 1, 2, and/or 3 months later to ask the questions listed in Appendix B.

5 BACKGROUND

Acne is a very common chronic inflammatory disease. Acne ranging from moderate to severe affects around 20% of young people. Acne continues to persist into the 20s for 64% of individuals and 30s for 43% of individuals [1].

There are systemic and topical treatments currently on the market for the treatment of acne. These products can cause severe side effects, thus new and innovative therapies are needed. Additionally, acne is known to cause significant psychological morbidity in patients [2].

Acne lesions are either noninflammatory (open and closed comedones, called whiteheads and blackheads) or inflammatory (papules and pustules) [2].

BioMimetix JV, LLC, has developed a topical gel and a topical cream formulation of BMX-010 for the treatment of inflammatory skin diseases, such as Acne. BMX-010 (MnTE-2-PyP) is a manganese (Mn) porphyrin drug; porphyrins are made up of 4 pyrrole rings connected by methine bridges. These molecules often form complexes with metals by incorporating them into the nucleus of the porphyrin structure, situated between the interiorly-located vertices of the pyrrole rings. Such Mn-porphyrin-based compounds are potent anti-inflammatory agents that can catalytically inactivate a range of reactive oxygen species, including peroxynitrite and superoxide anion [3,4].

BMX-010 (MnTE-2-PyP) exhibits extremely high enzymatic redox activity for a broad range of oxidant species including O₂-, H₂O₂, and ONOO- (ROS). The drug has catalytic antioxidant activity capable of scavenging ROS as well as the mimicking of superoxide dismutase. Unlike other antioxidants, this class of agents is catalytic and can repetitively eliminate ROS. BMX-010 acts as a scavenger in the cell cytoplasm, as in the context of reduced TACE oxidation [5] and yet functions as an oxidizer in the nucleus, inhibiting the reduction of the p50 subunit of NF-κB and effectively blocking DNA binding [6]. As a result of the complex mechanism of action, BMX-010 and other metalloporphyrin compounds exhibit an unexpected potency in inflammatory injury models at doses 100 to 1000 times less than would be expected if they were acting primarily as stoichiometric antioxidants [7,8]. BMX-010 and related compounds mechanism of action is reflected in diverse preclinical models.

T cells become hypo-responsive after BMX-010 treatment [5,9]. BMX-010 treatment promotes metabolic quiescence, impedes diabetogenic autoimmune responses by restricting the metabolic pathways for energy production and affects anabolic processes necessary for cell proliferation [10]. This metabolic reduction decreases T cell differentiation, returning T cells to stasis or quiescence, all while retaining viability [7,11,12]. A lowered aerobic glycolysis in T cells suggests the potential for treating chronic inflammatory dermatologic conditions, such as atopic dermatitis or psoriasis.

In pancreatic islet cells, oxidative stress develops during organ harvesting, during the isolation process, and during storage and transport. Isolation insults result in osmotic, mechanic ischemic, and oxidative stress for the islet cells. These events lead to increased production of pro-inflammatory cytokines and free radicals by pancreatic acinar cells, passenger leukocytes, and islet cells themselves, leading ultimately to β cell dysfunction and death. Therefore, the ability to

reduce these early nonspecific proinflammatory events (i.e., free radical generation and cytokine production) during islet cell isolation should afford increased β cell mass as well as improved and more stable metabolic function [13,14]. Experiments in such models show that BMX-010 modulates Th1 cells and effector cytokine production [5,8,9] and protects islets during isolation for transplantation [9,13].

In models of acute central nervous system injury and ischemic stroke, BMX-010 treatment reduces NF- κ B activation [6] and CD8 T cell effector function [12] enhancing neurologic function [16,17]. In cancer models, BMX-010 blocks HIF-1 activation, decreases hypoxia, reduces tumor-protective cytokine release and ultimately suppresses tumor growth [18]. HIF-1 is critical for facilitating glycolysis in times of low oxygen, and tumor cells depend heavily on glycolysis to survive.

In order to evaluate toxicity of the MnTE-2-PyP drug substance, a full good laboratory practice nonclinical safety assessment was conducted. BMX-010 was evaluated in *in vitro* genotoxicity studies, local tissue tolerance evaluation, safety pharmacology core battery studies, and single- and repeat-dose intravenous (IV) toxicity studies in mice and monkeys [13]. BMX-010 was determined not to be genotoxic or hemolytic, did not demonstrate flocculation or elicit adverse pharmacologic effects on respiration and the central nervous system, and had limited transitory effects on the cardiovascular system only at levels well above the therapeutic target dose. The IV clinical solution did not cause venous irritation in rabbits. The no observed adverse effect level (NOAEL) in mice was determined to be 10 mg/kg/day after 18 consecutive days of bolus IV dosing once daily (QD) in the morning. The NOAEL in monkeys after 14 days of bolus IV dosing in the morning was determined to be 5 mg/kg/day. At doses relevant to clinical use in humans, neither study revealed any indication of any specific target organ toxicity, including the classic heme porphyrin kidney, liver, CNS, or cardiac toxicities, or manganese toxicity. Mortality seen shortly after dosing in individual animals at higher doses was not accompanied by any organ or clinical pathology indications, suggesting a functional pharmacological-mediated effect.

Based on the demonstrated activity of BMX-010 to reverse persistent dermal inflammation, we believe adding BMX-001 as a topical therapy for patients with Rosacea, may be a relevant contribution to this disease model either as monotherapy or as combination therapy.

Completed Phase 1 safety studies on BMX-010 have indicated no identifiable toxicities.

6 STUDY OBJECTIVES

6.1 Primary Objectives

Part A

1. Determine whether the optimum frequency of topical application of BMX-010 0.03% is once per day or twice per day for a treatment interval of 7 to 28 days.
2. Determine whether the optimum frequency of topical application of BMX-010 0.1% is once per day or twice per day for a treatment interval of 7 to 28 days.
3. Determine if BMX-010 cream or gel provides better efficacy.
4. Evaluate the efficacy of BMX-010 0.03% in treatment of Acne Vulgaris.
5. Evaluate the efficacy of BMX-010 0.1% in treatment of Acne Vulgaris.

Part B

1. Evaluate the efficacy of BMX-010 compared to placebo in a randomized, double-blind trial.
2. Determine the percent of subjects showing a 2 grade improvement in IGA score after treatment with BMX-010 compared to Placebo.
3. Determine the percent of subjects showing a 2 grade improvement in IGA score with full or partial clearing (final IGA score of 1 or 0) after treatment with BMX-010 compared to Placebo.
4. Determine the time to full clearing of Acne Vulgaris after initiation of treatment with BMX-010.

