9 TREATMENT OF SUBJECTS

9.1 Treatments Administered

9.1.1 Phase 1/Phase 2 Cohorts

Part A

Cream or gel: BMX-010 0.03% or BMX-010 0.1% or Placebo QD
Cream or gel: BMX-010 0.03% or BMX-010 0.1% or Placebo BID

Part B

BMX-010 dose & formulation determined in Part A vs Placebo. QD or BID frequency as determined in Part A will be conducted.

In this study, up to 210 subjects will be enrolled.

In **Part A**, up to 60 subjects will be enrolled. Subjects will not be randomized and treatment concentration, formulation, and dosing frequency will be at the discretion of the clinical center investigator. All subjects will receive study drug at either 0.03% or 0.1% concentration. They will dose either QD or BID as indicated by the clinical center investigator during the baseline and other weekly visits throughout the study.

In **Part B**, up to 150 subjects will be enrolled. This will be a double-blind study, where the investigator and subject both will not know whether study drug or Placebo has been dispensed. Subjects will be randomized to BMX-010 or Placebo (2:1) in accordance with the randomization schedule. The Placebo cream is color-matched to the study drug, the Placebo gel is not. Up to 100 subjects will be randomized to BMX-010 and up to 50 subjects will be randomized to Placebo.

Although acne occurs on the face *and* trunk, efficacy assessment by IGA will be limited to the face as that is the most frequent site of involvement. However, the study product may be applied to all affected areas during this clinical trial.

When subjects apply QD, it can be applied any time of the day. When it is applied BID it should generally be applied 12 hours apart.

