40. US Department of Health and Human Services Food and Drug Administration Center for Drug Evaluation and Research (CDER). Acne Vulgaris: Establishing Effectiveness of Drugs Intended for Treatment Guidance for Industry. Rockville, MD: Office of Communications, Division of Drug Information. May 2018.
<https://www.fda.gov/downloads/Drugs/Guidances/UCM071292.pdf>

19 Appendix A: Patient Reported Outcome (PRO) Questions

Weekly Visit

1. How often are you applying the study drug?
 - Once a Day
 - Twice A Day
2. Did you apply the study product as instructed?
 - Yes
 - No
 - If no: clarify with comments
3. Would you like to apply the study drug more often?
 - Yes
 - No
4. Do you feel that your quality of life has improved from using the study drug?
 - Yes
 - No
5. How would you assess the change in your rash since your previous visit?
 - Worse
 - No change
 - A little better
 - Definitely better
 - Drastically better
 - Clear

**Clearing Questions- only to be asked if the Acne Vulgaris has cleared or partially cleared.
Indicate [] N/A if no clearing has occurred**

1. On approximately what date did the Acne Vulgaris clear?
2. Have any of your previously cleared lesion(s) come back? Yes/No
 - a. If Yes, on what date did it come back?
 - b. If Yes, where did it come back?
 - i. Same area as before
 - ii. New area, specify:

The following questions are for the last visit only

1. Do you feel that your quality of life has improved from using the study drug?
 - Yes
 - No

2. How would you assess the change in your rash since your previous visit?
 - Worse
 - No change
 - A little better
 - Definitely better
 - Drastically better
 - Clear

Clearing Questions- only to be asked if the rosacea has cleared or partially cleared.
Indicate [] N/A if no clearing has occurred

1. On approximately what date did the rosacea clear? _____

2. Have any of your previously cleared lesion(s) come back?

- Yes
- No

If Yes, on what date did it come back?

If Yes, where did it come back?

- Same area as before
- New area, specify:

Color Questions

1. Do you have any concerns about the color of the study product?
 - No concerns

- Mild concerns
- Major concerns

2. Did the study product stain (meaning the color stayed on after washing) your clothing/bedsheets, etc? Yes/No

20 Appendix B: Phone Follow-up Questions

1. What is the current status of your Acne?
2. Are you currently on any medications or treatments for controlling your Acne? If yes, obtain list.

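### Part B primary objective 4 (time to full clearing) names BMX-010 but no placebo comparator, so a one-arm description would satisfy it although both randomized arms are assessed on the same schedule

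*Protocol*

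**What the plan says.** Protocol Section 6.1 lists four primary objectives for Part B, and the Synopsis repeats them.

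- Objective 1: "Evaluate the efficacy of BMX-010 compared to placebo in a randomized, double-blind trial".
- Objective 2: "Determine the percent of subjects showing a 2 grade improvement in IGA score after treatment with BMX-010 compared to Placebo".
- Objective 3 adds to the two-grade improvement the requirement of "full or partial clearing (final IGA score of 1 or 0) after treatment with BMX-010 compared to Placebo".
- Objective 4: "Determine the time to full clearing of Acne Vulgaris after initiation of treatment with BMX-010".

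The Synopsis gives the allocation: "The randomization scheme is 2:1, study drug : Placebo". Section 9.1.1 gives the arm sizes: "Up to 100 subjects will be randomized to BMX-010 and up to 50 subjects will be randomized to Placebo". Section 7.2 sets visits at about Days 8, 15, 22, 29 and 43, and Table 4.a schedules an IGA at each of them without distinguishing the arms.

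Clearing appears in two other places. Section 7.2.1, on stopping dosing, ties it to the investigator's IGA of 0. Appendix A asks the subject: "On approximately what date did the Acne Vulgaris clear". Section 14 describes no analysis of time to clearing and leaves variable definitions and methods to the SAP.

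**The concern.** Three of the four primary objectives are explicitly comparative and the fourth is not. An analysis that follows objective 4 to the letter could report time to clearing on BMX-010 alone and comply with the Protocol.

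Such a result has no reference. The Protocol itself allows for acne that returns after clearing (Section 7.2.1 and the Appendix A clearing questions), so change over six weeks cannot be credited to the drug without a control. The placebo here is also the vehicle, which may act on the skin in its own right. One of the primary objectives of a randomized, placebo-controlled part would then be answered with a figure that says nothing about drug effect, while the data needed for the comparison sit in the same database.

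**Working it through.** **1. The wording side by side (Part B, Section 6.1)**

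| Objective | Endpoint named | Placebo named |
|---|---|---|
| 1 | none (efficacy in general) | yes |
| 2 | two-grade IGA improvement | yes |
| 3 | two-grade improvement with final IGA 0 or 1 | yes |
| 4 | time to full clearing | no |

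Objective 1 does not repair objective 4, because it names no endpoint.

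**2. The Protocol's own figure.** Up to 150 subjects at 2:1 gives 150 × 2/3 = 100 on BMX-010 and 150 × 1/3 = 50 on placebo. This reproduces Section 9.1.1. The Protocol states no alpha, power, clearing rate or event count for this endpoint.

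**3. What a one-arm result leaves open (illustration).** Assume 20 of 100 BMX-010 subjects clear. The exact 95% confidence interval is 12.7% to 29.2%, which describes clearing on drug and nothing more. The drug effect depends on the placebo rate. With a constant clearing rate in each arm, hazard ratio = ln(1 − p_drug) / ln(1 − p_placebo), where ln(0.80) = −0.2231:

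| Assumed placebo clearing | Difference | Hazard ratio | Total clearings, 100 × 0.20 + 50 × p_placebo |
|---|---|---|---|
| 5% | 15 points | −0.2231 / −0.0513 = 4.35 | 22.5 |
| 10% | 10 points | −0.2231 / −0.1054 = 2.12 | 25 |
| 20% | 0 points | 1.0 | 30 |

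The same BMX-010 result fits a large effect and no effect at all.

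**4. What the two-arm comparison could deliver.** Schoenfeld's formula is events = (1.960 + 0.842)² / [(2/3)(1/3)(ln HR)²]. Two-sided alpha of 0.05 and 80% power are assumed here. A hazard ratio above 1 means faster clearing on BMX-010.

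| Hazard ratio | Clearings needed for 80% power | Power with 30 clearings |
|---|---|---|
| 1.5 | 215 | 18% |
| 2.0 | 74 | 43% |
| 2.5 | 43 | 66% |
| 3.0 | 30 | 81% |

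The 215 clearings for a hazard ratio of 1.5 exceed the 150 subjects in Part B. Unless clearing is common or the effect large, the comparison is an estimate with a confidence interval and not a decisive test.

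**5. Resolution of the event time.** Nominal gaps between visits are 7 days up to Day 29 (1–8, 8–15, 15–22, 22–29) and then 43 − 29 = 14 days.

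**6. Whether the event is defined.** Three descriptions of clear skin differ:

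- The Synopsis IGA scale requires that there be neither inflammatory nor noninflammatory lesions.
- Section 7.2.1 cites IGA = 0, then treats acne as clear when inflammatory signs are absent.
- The Section 11.1 scale refers to papules, pustules and absence of erythema, while the text above it allows residual erythema at a score of Clear.

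A subject with comedones but no inflammatory lesions is clear under some of these and not under others, so the date of clearing depends on which one is applied.

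**The case against.** The strongest reply is that this is loose drafting. Objective 4 does not expressly exclude placebo subjects, and Part B secondary objectives 1 and 3 also omit the comparator. Objective 1 already makes efficacy against placebo primary, both arms follow the same visits, and Section 14 defers methods for all objectives to a SAP that may well add the comparison. The trial is exploratory, its sample size has no statistical basis, and a descriptive time on drug has planning value.

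Much of this stands. That the measurement is confined to BMX-010 is an inference from the wording, supported by the contrast with objectives 1 to 3. The choice of estimator and test belongs in the SAP. Whether a primary objective is comparative, however, is settled in the Protocol, and a SAP faithful to objective 4 need not use the placebo arm.

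Two stronger readings are tempting, and the text supports neither.

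- A reader might infer that the objective means the time among subjects who clear, and criticise the mean of that subset. The text has no such condition and names no mean; it is ordinary time-to-event wording.
- A reader might infer from Appendix A that the subject's recall is the only source of a clearing date. It is not: the investigator scores IGA at every visit, Section 7.2.1 links clearing to that score, and nothing makes the recalled date the source for objective 4.

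**Conclusion.** The point holds as a matter of wording. Part B primary objective 4 lacks the placebo comparator that the other three carry, and it can be met by a one-arm description that cannot show a drug effect. This rests on the text of the Synopsis and Section 6.1 and on the absence of a comparison for this endpoint elsewhere in the Protocol. The SAP is not at hand and may add one.

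The weight is moderate. The data for the comparison will be collected in both arms, objectives 2 and 3 keep their own contrasts, and the trial makes no powered claim. The clearing rates, hazard ratios, alpha and power in the working are assumptions that show scale; none comes from the Protocol.

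**What to change.** Reword objective 4 in both the Synopsis and Section 6.1, for example: *Compare the time from first application to full clearing (first visit with investigator-assessed IGA = 0) between BMX-010 and Placebo.* State that subjects who do not clear are censored at their last IGA, and that the recalled date in Appendix A is supportive only. The remaining analysis detail can stay in the SAP, which should allow for event times known to about one week up to Day 29 and two weeks from Day 29 to Day 43.

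Before that, reconcile the descriptions of clear skin in the Synopsis, Section 7.2.1 and Section 11.1, so that IGA = 0 denotes one state. The sponsor must decide which description applies.

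The cost is one sentence changed in two places plus that reconciliation. No subjects, visits or assessments are added.
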